3. THEORETICAL FRAMEWORK

The Behaviour Change Wheel (BCW) was specifically developed to examine Health-related Behaviour Change arising from an intervention (Michie et al. 2011). It represents a collection of mini-frameworks to link intervention function and policy categories to behaviour (See **Fig 1**, Appendix 5.). The COM-B system forms the ‘hub’ of the BCW (See **Fig 2**, Appendix 5.) and identifies three core components predicting an individual’s health behaviour change arising from interventions:

- **Capability:** The individual’s psychological and physical capacity to engage in the activity. This includes having the necessary knowledge and skills.
- **Opportunity:** Factors that lie outside of the individual that make the behaviour possible or prompt it.
- **Motivation:** Brain processes that energise and direct behaviour. This includes habitual processes and emotional responses as well as analytical decision making.

The COM-B system is gaining substantial interest across numerous health conditions and has been specifically identified as a desired approach to the conceptualisation of Health Behaviour Change in audiology research (Coulson et al. 2016).

The Theoretical Domains Framework (TDF) is a validated integrative framework of theories of behaviour change, developed by psychological theorists, in collaboration with health service researchers and health psychologists (Cane et al. 2012). The TDF enables theoretical constructs relating to behaviour change (grouped into domains) to be mapped directly to the COM-B system components of Capability, Opportunity and Motivation (See **Fig 3**, Appendix 5.). In this research, the TDF will be used as a framework by which to thematically organise data. This will enable data to be mapped to the COM-B system to identify the determinants of health behaviour change arising from the Ida Telecare tools.

The Behaviour Change Technique (BCT) Taxonomy v1 (Michie et al. 2013) is an extensive, consensually agreed hierarchically structured taxonomy of techniques used in behaviour change interventions (See **Fig 4**, Appendix 5.). A Behaviour Change Technique is an observable, replicable and irreducible component of an intervention designed to alter or redirect causal processes that regulate behaviour (an “active ingredient”, Michie et al. 2013, pp.82).

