4.1. Objectives

Sub-study 1: Feasibility

Specific objectives:

1. Implementation (feasibility) of the tools: ***How and when are the Ida telecare tools used by patients?***
 - a. Establish study recruitment rates.
 - b. Examine usability of the tools using Think Aloud techniques.
 - c. Quantify uptake, usability and completeness of the tools by patients.
 - d. Identify whether the tools used by patients in-between appointments/in place of appointments (e.g. in place of the optional follow-up).
2. Mechanisms of impact: ***What mechanisms of benefit do the tools target?***
 - a. What are the key mechanisms targeted by the tools (e.g. knowledge or skill, motivation) and are these obvious to patients and audiologists?
 - b. How might we expect the targeted mechanisms to improve patient experiences and outcomes (e.g. improved self-efficacy, readiness to take action) and what might the best measures be to capture success?
3. Contextual factors: ***What influences patients’ use of the tools?***
 - a. Explore at what stage in the pathway the tools might be most useful to patients
 - b. Identify key barriers to use and how might these be overcome.
 - c. Establish whether there any informational/support gaps or additional tool requirements.

Ida Telecare

IRAS: 232078

Sub-study 2: Effectiveness

Specific objectives:

1. To evaluate the impact of using the Tool on hearing aid uptake, use, self-efficacy and patient's readiness to manage their hearing loss (Quantitative).
2. To use the COM-B model to investigate the views and experiences of patients and audiologists in terms of how the Tool was used in the audiological rehabilitation process (Qualitative).

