- i) ensure data held about patients' use of the Telecare tools is accurate and complete and to obtain any outstanding .PDF files for completed tools,
- ii) establish whether or not the tools were discussed with the audiologist during the appointment,
- iii) establish the outcome of the appointment (i.e. for hearing assessment appointments: no treatment, onward referral to ENT, or prescribed hearing aids), and
- iv) establish whether or not patients have attended or booked further appointments e.g. 'repair' appointments (additional audiological care and hearing aid maintenance), or an optional follow-up.

For those participants choosing not to opt-in to a follow-up appointment with an audiologist, we will identify whether any of the Ida telecare tools were used in place of that formal appointment.

2. Mechanisms of impact: BCT Taxonomy coding

Each of the Ida telecare tools will be examined in terms of their intended mechanisms of action for bringing about health behaviour change by the research team. First, the CI will speak directly with the Ida institute to gather details about the development of the tools and the underpinning theory guiding

Ida Telecare

IRAS: 232078

them. The research team will then use BCT Taxonomy (Michie et al., 2013) to code the “active ingredients” of each telecare tool. The BCT Taxonomy enables users to specify the smallest components of behaviour change interventions that can bring about change. By identifying and defining the targeted behaviour change components of the Ida telecare tools, relevant and appropriate outcome measures can be proposed for efficacy studies that will be sensitive to those mechanisms of benefit.

3. Contextual Factors: Semi-structured interviews

Semi-structured interviews with patients and audiologists will be conducted by a member of the research team to gather in-depth information about:

- why patients decided to use the telecare tools
- what benefit(s) both patients and audiologists attributed to use of the tools
- at what stage in the pathway the tools might be most relevant and/or useful to patients
- any additional information or support that might have been useful to include within the tools, or any extra tools or activities that might be considered
- whether patients experienced any barriers to use of the tools and how these might be addressed.

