Interview schedules have been created by the research team and will be reviewed by patient representatives to ensure questions are clear and relevant to patients. Data collection will cease once data saturation has been reached. A sample size of $n \leq 15$ has been found to be generally sufficient to achieve data saturation for semi-structured interviews (Guest et al. 2006).

Interviews will be audio recorded and anonymously transcribed verbatim. Transcripts will be analysed by the research team using inductive thematic analysis. Generated codes and themes relating to benefit(s) of the interventions and additional suggested content will be organised using the TDF and mapped to the COM-B system to examine how the telecare tools might influence health behaviours according to individuals’ Capability, Opportunity and Motivation.

Sub-study 2: Effectiveness

1. Impact of the ‘Why Improve My Hearing?’ Ida telecare tool

Enrolled patients to this sub-study will be minimised to one of two arms: (i) treatment-as-usual, patients receiving standard care only, and (ii) experimental pathway, patients receive standard care plus access to the Ida Telecare ‘Why Improve My Hearing?’ tool online prior to their first assessment. Minimised allocation will be based on gender (male/female) and age: younger (<70 years old)/older (70 years old or greater). The minimisation will be generated and maintained by a researcher not directly involved in patient recruitment or testing (EH, [name]), using OxMaR software (O’Callaghan 2014).

The following validated outcome measures will be completed online or via post in accordance with the patients’ preference:

Baseline – before completion of the ‘Why Improve My Hearing?’ Ida telecare tool and immediately post hearing assessment appointment:

- *Measure of Audiologic Rehabilitation Self-efficacy for Hearing Aids (MARS-HA)* (West and Smith 2007). Includes four subscales: basic handling, advanced handling, adjustment to hearing aids, and aided listening skills. Respondents indicate how confident they are that they

could do the things described on an 11-point scale (0%=cannot do this, to 100%=certain I can do this).

- *Short-form Patient Activation Measure (PAM)* (Hibbard et al. 2005). A 13-item measure that assesses patient knowledge, skill, and confidence for self-management of their health. Each item is scored on a four-point ordinal scale (0 = disagree strongly to 3 = agree strongly).

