Interviews with patients and audiologists will be audio recorded and anonymously transcribed verbatim. Transcripts will be subjected to inductive thematic analysis by the Study Co-ordinator, guided by the research questions. Generated codes and themes will be categorised according to the TDF and mapped to the COM-B system to examine if, and if so how, the intervention prompted changes in health behaviours relative to individuals' Capability, Opportunity and Motivation.

Ida Telecare

IRAS: 232078

Study timeline

	2017					2018							
	study	Sep	Oct	Nov	Dec	Jan	Feb	Mar	Apr	May	Jun	Jul	Aug
Study set-up and recruitment													
Seek approvals (Ethics/sponsor)	■												
Study setup	■	■											
NAS Audiologist briefing		■											
Recruitment of NAS direct referral patients		■	■	■	■	■	■						
Feasibility													
Quantitative data collection (initial assessment)			■	■	■	■	■	■					
Quantitative data collection (fitting)				■	■	■	■	■	■				
Qualitative Think Aloud & concurrent analyses						■	■	■	■	■			
Quantitative data collection (follow-up)							■	■	■	■	■	■	■
BCT Taxonomy coding								■	■	■			
Qualitative semi-structured interviews									■	■	■		
Qualitative interview transcription & analysis										■	■	■	
Quantitative data analysis										■	■	■	
Write-up and dissemination											■	■	■
Effectiveness													
Quantitative data collection (initial assessment)			■	■	■	■	■	■					
Qualitative semi-structured interviews						■	■	■	■				
Qualitative analysis using COM-B									■	■	■		
Quantitative data collection (6-weeks post-fit)						■	■	■	■	■	■	■	■
Quantitative data analysis											■	■	■
Write-up and dissemination												■	■

Data Storage and Access

All data will be stored in password protected databases (e.g. SPSS) or files on a secure part of the NIHR Nottingham BRC network that is accessed only by members of the research team. All paper files will be stored in locked cupboards within the NIHR Nottingham BRC. Audio and video recordings will be securely stored electronically for a period of no more than 18 months. Arrangements will be made for the confidential destruction of these recordings within 6 months of the planned study end-date of 31st August 2018.

Anonymised data arising from this research may be shared with other genuine researchers.

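### Sub-study 1 names only benefit and suggested-content codes for the TDF/COM-B mapping, and no listed topic covers drawbacks or audiologists' own barriers, so that mapping is tilted towards benefits

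*Protocol*

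**What the plan says.** Section 5 of the protocol, sub-study 1, part 3 (Contextual Factors), plans semi-structured interviews with patients and audiologists and lists five topics. Three matter most here:

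- Use: "why patients decided to use the telecare tools".
- Benefits: "what benefit(s) both patients and audiologists attributed to use of the tools".
- Barriers: "whether patients experienced any barriers to use of the tools and how these might be addressed".

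The other two are the pathway stage at which the tools are most useful, and any information, support or tools that were missing.

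The first analysis step is open: "Transcripts will be analysed by the research team using inductive thematic analysis". The second is selective: "Generated codes and themes relating to benefit(s) of the interventions and additional suggested content will be organised using the TDF", followed by mapping to COM-B to examine how the tools might influence health behaviours.

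Three other places bear on this:

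- Section 4.1, objective 3b for sub-study 1: "Identify key barriers to use and how might these be overcome".
- Section 3, on the purpose of organising data by the TDF: "This will enable data to be mapped to the COM-B system to identify the determinants of health behaviour change", with no limit to favourable data.
- Section 5, sub-study 2, part 2: "Generated codes and themes will be categorised according to the TDF and mapped to the COM-B system", again with no limit.

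**The concern.** An analysis rule that selects findings by their direction before the interpretive step shapes what that step can show. In sub-study 1 the COM-B mapping is where interview findings are turned into an account of how the tools act on Capability, Opportunity and Motivation. If benefits and suggested additions are the only codes sent there, a theme that a tool confused or discouraged a patient has no stated way in.

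The interview topics lean the same way. Both groups are asked about benefits, nobody is asked about drawbacks, and barriers are worded as those that patients met. Section 4.2 says the study is meant to inform implementation in a routine NHS service. For that purpose, audiologists' own obstacles and the COM-B component behind each barrier are useful to know.

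**Working it through.** No arithmetic beyond a count applies. The check sets the passages side by side.

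**Step 1. Topics against the mapping rule (section 5, sub-study 1, part 3).**

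| Listed topic | Worded for | Named for TDF/COM-B |
|---|---|---|
| Reasons for using the tools | patients' decision to use | no |
| Benefits | patients and audiologists | yes |
| Most useful pathway stage | patients | no |
| Missing information, support or tools | no group named | yes, as suggested content |
| Barriers and remedies | barriers patients met | no |

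Two of the five topics have a named route into the mapping, and 5 − 2 = 3 do not. None of the five names drawbacks, audiologists' own barriers, or reasons for not using the tools.

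**Step 2. Mapping rule against the rest of the protocol.**

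- Section 3 describes the TDF as a way of organising the data so that determinants of behaviour change can be identified. Hindrances are determinants as much as helps are.
- Sub-study 2 sends all generated codes and themes to the TDF and COM-B, and asks whether, and if so how, the intervention prompted change. Sub-study 1 asks only how. No reason is given for the difference. The contrast concerns the mapping rule only, because sub-study 2's topic list also names benefits and no drawbacks.

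**Step 3. Is there another route into COM-B for unfavourable findings in sub-study 1?** Section 3 also maps the behaviour change technique codes to COM-B. According to section 5, part 2, those codes describe how each tool is meant to work. They are not patient experience, so they do not supply what the interview mapping leaves out.

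**Step 4. What unfavourable information is kept elsewhere?** Patient barriers are an objective (3b), a listed topic and part of the unrestricted inductive coding. Suggested content can expose gaps and is mapped. Section 5, part 1, adds Think Aloud usability data and recorded personal or technical reasons for being unable to take part. Section 4.1, objective 1c, adds uptake and completeness.

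**Result.** The selection acts on the mapping. It does not act on the collection or coding of patient barriers. On the audiologist side, the gap lies in the listed topics.

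**The case against.** The strongest reply is that two questions are being merged. Objective 3 asks what influences patients' use of the tools. The mapping has a different stated purpose, namely how the tools might influence health behaviours, and the determinants in section 3 are likewise those of behaviour change arising from the tools. A barrier to use, such as having no computer, is not an effect of a tool on behaviour, so a mapping of mechanisms could reasonably leave it out. Section 3's paragraph on the feasibility study mentions only the technique codes for COM-B and does not promise that every interview code will be mapped. This has force for barriers to access. It does not cover unhelpful influences on behaviour, which belong to the mapping's own question and still have no named route into it.

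A second reply concerns audiologists. Objective 3 is framed around patients' use, all five topics are introduced for interviews with both groups, and objective 5 in the study summary neutrally seeks audiologists' views on acceptability, use and relevance. The interview schedules exist but are not shown, and semi-structured interviews allow probing. This stands as a limit: the protocol shows a gap in its listed topics and does not show that the questions will go unasked.

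Two stronger readings should be resisted:

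- **That the account of tool use can only come out favourable, or that its direction is fixed.** The sources in step 4 of the working rule this out.
- **That the background's suggestion of saved appointment time makes audiologist time an obvious missing topic here.** That passage concerns the 'Why Improve My Hearing?' tool, which sub-study 2 examines. There, audiologists are asked how it was used within the appointment.

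**Conclusion.** The point holds in a limited form and is minor. The protocol states a selective mapping rule for sub-study 1 that departs, without explanation, from its own general statement on the TDF and from its practice in sub-study 2. Its listed topics are also asymmetric between benefits on one side and drawbacks and audiologist barriers on the other. The COM-B account of how the tools influence behaviour is tilted towards benefits as a result. The tilt cannot be put as a number.

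The conclusion assumes that the mapping sentence means what it says, so that codes it does not name are not mapped. It also assumes that the topic list is a fair summary of the interview schedules. Barriers remain available as themes, objective 3b can still be answered, and no quantitative outcome of the randomised comparison is affected.

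**What to change.** 1. In section 5, sub-study 1, part 3, delete the phrase that limits the codes to benefits and suggested content. All codes and themes, including barriers and unhelpful effects, would then be organised by the TDF and mapped to COM-B, as in sub-study 2.
2. In the topic list of the same part, widen the benefits topic to benefits and drawbacks, and the barriers topic to barriers experienced by patients or audiologists. Carry both changes into the interview schedules before the patient representatives review them.

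The cost is one phrase deleted, two prompts reworded and slightly more coding work. No extra interviews are needed.

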Continuous data (e.g. age) will be summarised using means and standard deviations, whereas categorical data (e.g. gender) will be summarised using percentages. Medians and quartiles will be reported for non-parametric data, and means, standard deviations and 95% confidence intervals for normally-distributed parametric data. Normality of continuous data will be assessed using histogram plots and the Shapiro Wilk Test. For each measure, the difference between arms will be examined

Ida Telecare

IRAS: 232078

using parametric (e.g. T-test) or non-parametric (e.g. Wilcoxon Rank Sum Test) statistics where appropriate. For categorical data, Chi-square test will be used, and Fishers exact test if any of the cells are less than 5. Statistical significance will be set at $p=0.05$ and corrected (e.g. Bonferroni) for multiple comparisons. As outcome data will be collected after the intervention period, no interim analyses will be performed.

2. *Patient and Audiologist views and experiences*

For the alternative pathway only:

A sub-set (6/28) of hearing assessment appointments will be video recorded to enable a detailed assessment of how the tools were jointly used by the patient and audiologist. The videos will also be shared with the research funders to identify how the tools might be improved or amended to better suit patients' needs in future.

A sample of patients and audiologists will be recruited from the alternative pathway using maximum variation sampling (Patton 1990), to take part in semi-structured interviews with a member of the research team. Interviews will examine patients and audiologists perceptions and experiences of using the 'Why Improve My Hearing?' telecare tool, specifically:

- what influenced patients use of the tool
- how, when and where the tool was used by patients in preparation for their hearing assessment appointment
- how the tool was used jointly by audiologists and patients within the clinical appointment
- what benefit(s) patients and audiologists attributed to use of the tool

The interview schedules will be designed to provide an in-depth understanding, and will be reviewed by patient representatives to ensure clarity of concepts and relevance to patients. Data collection will cease once data saturation has been reached.

Interviews with patients and audiologists will be audio recorded and anonymously transcribed verbatim. Transcripts will be subjected to inductive thematic analysis by the Study Co-ordinator, guided by the research questions. Generated codes and themes will be categorised according to the TDF and mapped to the COM-B system to examine if, and if so how, the intervention prompted changes in health behaviours relative to individuals' Capability, Opportunity and Motivation.

Ida Telecare

IRAS: 232078

Study timeline

	2017					2018							
	study	Sep	Oct	Nov	Dec	Jan	Feb	Mar	Apr	May	Jun	Jul	Aug
Study set-up and recruitment													
Seek approvals (Ethics/sponsor)	■												
Study setup	■	■											
NAS Audiologist briefing		■											
Recruitment of NAS direct referral patients		■	■	■	■	■	■						
Feasibility													
Quantitative data collection (initial assessment)			■	■	■	■	■	■					
Quantitative data collection (fitting)				■	■	■	■	■	■				
Qualitative Think Aloud & concurrent analyses						■	■	■	■	■			
Quantitative data collection (follow-up)							■	■	■	■	■	■	■
BCT Taxonomy coding								■	■	■			
Qualitative semi-structured interviews									■	■	■		
Qualitative interview transcription & analysis										■	■	■	
Quantitative data analysis										■	■	■	
Write-up and dissemination											■	■	■
Effectiveness													
Quantitative data collection (initial assessment)			■	■	■	■	■	■					
Qualitative semi-structured interviews						■	■	■	■				
Qualitative analysis using COM-B									■	■	■		
Quantitative data collection (6-weeks post-fit)						■	■	■	■	■	■	■	■
Quantitative data analysis											■	■	■
Write-up and dissemination												■	■

Data Storage and Access

All data will be stored in password protected databases (e.g. SPSS) or files on a secure part of the NIHR Nottingham BRC network that is accessed only by members of the research team. All paper files will be stored in locked cupboards within the NIHR Nottingham BRC. Audio and video recordings will be securely stored electronically for a period of no more than 18 months. Arrangements will be made for the confidential destruction of these recordings within 6 months of the planned study end-date of 31st August 2018.

Anonymised data arising from this research may be shared with other genuine researchers.

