7.2. Sampling

7.2.1. Size of sample

Sub-study 1: Feasibility

- Quantitative: Not applicable

One of the main aims of this Arm is to identify recruitment rates/intervention take-up in this population.

- Qualitative:
 - Think Aloud n=6-8 patients

Data collection will cease once data saturation has been reached. A sample size of 6-8 has been found to be generally sufficient to achieve data saturation for Think Aloud techniques (Henshaw et al. 2017).

- Semi-structured interviews with patients and audiologists: $n \leq 15$

Data collection will cease once data saturation has been reached (Guest et al. 2006).

Sub-study 2: Effectiveness

- Quantitative: n=56 participants (n=28 per arm)

In order to detect a 10% change in MARS-HA (smallest possible change) at a power of 80% and type II error rate of 5%, a total of 50 participants are required, 25 in each arm. This was calculated using a standard deviation for global MARS-HA scores derived from (Ferguson et al. 2016). As outcome measures will be taken immediately post-assessment, it is expected that fewer than usual participants will fail to complete outcome measures. Hence, a conservative attrition rate of 15% has been used, thus accounting for attrition, a total of 56 participants (28 per arm) will be recruited.

Ida Telecare

IRAS: 232078

- Qualitative: Semi-structured interviews with patients and audiologists

Data collection will cease once data saturation has been reached.

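### The only arm comparisons named for continuous outcomes are two-sample tests chosen after a normality check, with no stated use of the baseline scores or minimisation factors: valid, but inefficient

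*Protocol*

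**What the plan says.** The quantitative part of sub-study 2 in Protocol section 5 is the only text on the arm comparison.

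- **Selecting the method:** "Normality of continuous data will be assessed using histogram plots and the Shapiro Wilk Test". Each measure is then compared between arms "using parametric (e.g. T-test) or non-parametric (e.g. Wilcoxon Rank Sum Test) statistics where appropriate". Significance is set at 0.05, "corrected (e.g. Bonferroni) for multiple comparisons".
- **Baseline data:** MARS-HA, PAM, ECHO, SPaRQ, HHIE, GHABP Part I and the readiness questionnaire are taken before the tool is used and again after the appointment. The heading of that list ends "Ida telecare tool and immediately post hearing assessment appointment". MARS-HA, PAM, SPaRQ and HHIE are repeated 10-12 weeks after fitting.
- **Allocation:** "Minimised allocation will be based on gender (male/female) and age: younger (<70 years old)/older (70 years old or greater").
- **Sample size (section 7.2.1):** "In order to detect a 10% change in MARS-HA (smallest possible change"), 25 per arm, raised to 28 per arm for 15% attrition. The SD is cited but not printed: "This was calculated using a standard deviation for global MARS-HA scores derived from".

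No covariate, change score or regression model is named anywhere in the protocol.

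**The concern.** Three features of the stated analysis deserve attention in a trial of 56 patients.

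1. **Baseline scores.** With small arms, a chance difference in self-efficacy at baseline is likely to be appreciable. A two-sample test on the post-assessment score carries the correlated part of that difference into the result. It also leaves in the error term the variation that baseline would explain.
2. **Minimisation factors.** Minimisation balances gender and age group. If these predict outcome, a test that omits them overstates the standard error.
3. **Selection of the test.** Letting the trial data choose between a t-test and a rank-sum test lets the quantity being estimated differ by measure and time point. Section 5 promises 95% confidence intervals only for normally distributed data, so an outcome sent to the rank test may have no interval for the size of the effect. Normality of raw scores is also not the assumption that matters; the residuals of the fitted model are.

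At stake are precision and interpretability, not validity.

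**Working it through.** **Inputs from the Protocol.** Difference of 10 points on the 0-100% MARS-HA scale; 80% power; 25 evaluable per arm; 28 recruited per arm; 15% attrition (section 7.2.1). Section 7.2.1 reads "at a power of 80% and type II error rate of 5"%. A 5% type II error would contradict 80% power, so the 5% is read as the significance level, taken as two-sided.

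**Assumed inputs.** The SD and the baseline-to-post correlation r are not in the document. The SD is back-solved and r is shown at 0.3, 0.5 and 0.7.

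**Step 1: the plan's own figure.** Without the SD, 25 per arm cannot be checked independently. The SD that makes it correct is:

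- normal approximation: 10 / [(1.960 + 0.842) × √(2/25)] = 12.6
- exact t: 12.37, which gives 80.0% power at 25 per arm by construction

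The exact-t value is used below.

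**Step 2: completers.** 28 × 0.85 = 23.8 per arm.

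**Step 3: unadjusted test.** Standard error = 12.37 × √(2/23.8) = 3.58. Noncentrality = 10/3.58 = 2.79 on 45.6 degrees of freedom. Power is 78.0%, and the difference detectable with 80% power is 10.3 points.

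**Step 4: ANCOVA.** Residual SD = 12.37 × √(1 − r²). Degrees of freedom = 2 × 23.8 − 5 = 42.6, charging one each for baseline, gender and age group.

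| r | Residual SD | Standard error | Power for 10 points | Detectable at 80% |
|---|---|---|---|---|
| none (t-test) | 12.4 | 3.58 | 78.0% | 10.3 |
| 0.3 | 11.8 | 3.42 | 81.5% | 9.8 |
| 0.5 | 10.7 | 3.10 | 88.3% | 8.9 |
| 0.7 | 8.8 | 2.56 | 96.8% | 7.3 |

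Power returns to 80% once r exceeds about 0.23.

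**Step 5: chance imbalance.** The baseline difference between arms has the same standard error, 3.58 points, if the baseline SD is also 12.37. A gap of more than 5 points, half the target effect, has probability 2 × [1 − Φ(5/3.58)] = about 16%.

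**Step 6: change scores.** If the 10% change means change from baseline, the SD is 12.37 × √(2 − 2r). Power at 23.8 per arm is 64%, 78% and 94% at r = 0.3, 0.5 and 0.7, below ANCOVA in each case.

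**Step 7: minimisation factors.** In 5,000 simulated trials per setting (50 patients, assumed biased coin of 0.8, nominal 5%), the unadjusted t-test had type I error of about 5.3%, 3.8% and 3.0% when the two factors explained 0%, 10% and 20% of the variance. It is conservative only when the factors are prognostic.

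**Step 8: multiplicity.** The powers above are before correction. As an illustration at 25 per arm with Bonferroni over 7 measures, power is 52% unadjusted, against 69% at r = 0.5 and 88% at r = 0.7 with ANCOVA on baseline.

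**The case against.** The strongest reply is that the protocol gives the tests as examples, to be used where appropriate, and that covariates are commonly left to a statistical analysis plan, which is not at hand. On this view nothing is contradicted, and an unadjusted test is legitimate. Part of this stands: the planned test is valid, and the text does not forbid adjustment. But section 5 is not silent. It names the kind of comparison and how to choose within it, and both named options are unadjusted as written. Replacing a stated method differs from asking for missing detail.

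A reader might infer more than the document supports:

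- **That a substantial loss of power is established.** It is not. It depends on r and on a back-solved SD. At r = 0.3 the gain is about 3.5 percentage points.
- **That baseline is definitely ignored.** Section 7.2.1 speaks of a change in MARS-HA, and section 5 does not say whether post scores or changes are compared. The use of baseline is unspecified rather than ruled out, and a change score would still be less efficient than ANCOVA.
- **That standard errors are certainly too large.** This holds only if gender and age group predict outcome, which the document does not say.
- **That Shapiro-Wilk alone decides the test.** Histograms accompany it.
- **That baseline adjustment can apply to every outcome.** Data-logged use, GHABP Part II and the outpatient survey have no baseline of the same measure. For SADL there is only ECHO, a companion instrument on expectations rather than satisfaction.

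**Conclusion.** The point holds as one of efficiency and clarity. The arm comparison in section 5 is valid, but it names no use of baseline scores or minimisation factors and lets the effect measure vary by outcome. On MARS-HA, with an SD of about 12.4 implied by 25 per arm, 23.8 completers per arm and two-sided 0.05 before multiplicity correction, ANCOVA would raise power for 10 points from about 78% to about 82%, 88% or 97% at assumed correlations of 0.3, 0.5 or 0.7. A correlation of 0.5 or more is plausible for one questionnaire repeated around a single appointment, but remains an assumption. Most of the gain comes from the baseline score. The minimisation factors matter mainly for correct standard errors, and only if they are prognostic. The change should be made, but the trial is not invalid without it.

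**What to change.** Replace the sentence on the comparison of continuous outcomes in section 5 with wording to this effect:

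- **Baseline of the same measure available** (MARS-HA, PAM, ECHO, SPaRQ, HHIE, GHABP Part I, and readiness if scored as continuous): ANCOVA with arm, baseline score, gender and age group (<70/70+), reporting the adjusted mean difference and 95% confidence interval.
- **No such baseline** (data-logged hearing aid use, GHABP Part II, SADL, outpatient survey): linear model with arm, gender and age group, reporting the same quantities. Baseline ECHO is optional as a covariate for SADL.
- **Distribution:** no normality test on raw scores selects the primary method. Check residuals, use robust or bootstrap intervals if needed, and keep the rank-sum test as a sensitivity analysis.

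Also reconcile Appendix 2 with section 5. The example schedule marks MARS-HA, PAM, ECHO and HHIE only at the initial assessment and omits SPaRQ and readiness, whereas section 5 requires them before the tool is used. ANCOVA depends on that earlier collection taking place.

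The cost is protocol wording and up to three extra model terms. It needs no extra patients and, provided baseline is collected as section 5 states, no extra data.
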